11.10.6. Safety Figures

Safety: Figures					
No.	Population	IDSL No. / E.G. Shell	Title	Programming Notes	Delivery Priority
Labs					
2.01	Safety	SAF_F1	Individual Subject Plot - Hematology & Clinical Chemistry Selected Parameters		FA (SAC)
Epstein-Barr Virus Viral Load					
2.02	Safety	EFF_F2 (with different error bars, see notes)	Geometric Mean (+/- CV%): Epstein-Barr Virus Viral Load	
 X-axis: time Y-Axis: Geometric Mean Load (semi-log) Show error bars at $(1+CV\%) * \text{GeoMean}$ and $\text{GeoMean}/(1+CV\%)$ Line by group 	FA (SAC)

11.10.7. Efficacy Tables

Efficacy : Tables					
No.	Population	IDSL / TST ID / Example Shell	Title	Programming Notes	Deliverable [Priority]
Mixed Meal Tolerance Test : Weighted Mean AUC(0-120 mins) C-Peptide & Glucose					
3.01.	ITT (Treated)	Non-Standard EFF_T1	Summary Statistics (Absolute and Change from Baseline) : C-Peptide & Glucose Weighted Mean AUC(0-120 mins) from Mixed Meal Tolerance Test		FA (SAC)
3.02.	ITT (Treated)	Non-Standard EFF_T2	Summary of Statistical Analysis (MMRM) Results of Change from Baseline : C-Peptide & Glucose Weighted Mean AUC(0-120 mins) from Mixed Meal Tolerance Test	
 Include related estimated LSMeans and treatment differences. 	FA (SAC)
3.03.	Fully Treated	Non-Standard EFF_T2	Summary of Statistical Analysis (MMRM) Results of Change from Baseline : C-Peptide & Glucose Weighted Mean AUC(0-120 mins) from Mixed Meal Tolerance Test	
 Include related estimated LSMeans and treatment differences. 	FA (SAC)
Clamp (Hyperglycaemic Phase) : Weighted Mean AUC(60-140) C-Peptide & Glucose					

3.04.	ITT (Treated)	Non-Standard EFF_T1	Summary Statistics (Absolute and Change from Baseline) : C-Peptide and Glucose Weighted Mean AUCs (60-140 mins) from Hyperglycemic Clamp Test		FA (SAC)
3.05.	ITT (Treated)	Non-Standard EFF_T2	Summary of Statistical Analysis (MMRM) Results of Change from Baseline : C-Peptide and Glucose Weighted Mean AUCs (60-140 mins) from Hyperglycemic Clamp Test	
 • Include related estimated LSMeans and treatment differences. 	FA (SAC)
3.06.	Fully Treated	Non-Standard EFF_T2	Summary of Statistical Analysis (MMRM) Results of Change from Baseline : C-Peptide and Glucose Weighted Mean AUCs (60-140 mins) from Hyperglycemic Clamp Test	
 • Include related estimated LSMeans and treatment differences. 	FA (SAC)
CLAMP (Insulin Sensitivity Index)					
3.07.	ITT (Treated)	Non-Standard EFF_T1	Summary Statistics (Absolute and Change from Baseline) : Insulin Sensitivity Index from Hyperglycemic Clamp Test		FA (SAC)
3.08.	ITT (Treated)	Non-Standard EFF_T2	Summary of Statistical Analysis (MMRM) Results of Change from Baseline : Insulin Sensitivity Index from Hyperglycemic Clamp Test	Include related estimated LSMeans and treatment differences.	FA (SAC)
Mean Daily Insulin Use					
3.09.	ITT (Treated)	Non-Standard EFF_T1	Summary Statistics: (Absolute, Change from Baseline and Percentage Change from Baseline) : Mean Daily Insulin Use	
 • Please add percentage change from baseline to the shell (as BY) 	FA (SAC)
3.10.	ITT (Treated)	Non-Standard EFF_T2	Summary of Statistical Analysis (MMRM) Results of Change from Baseline : Mean Daily Insulin Use	Include related estimated LSMeans and treatment differences.	FA (SAC)
%HbA1c					

3.11.	ITT (Treated)	Non-Standard EFF_T1	Summary Statistics (Absolute and Change from Baseline) : %HbA1c		FA (SAC)
3.12.	ITT (Treated)	Non-Standard EFF_T2	Summary of Statistical Analysis (MMRM) Results of Change from Baseline: %HbA1c	Include related estimated LSMeans and treatment differences.	FA (SAC)
Body Weight					
3.13.	ITT (Treated)	Non-Standard EFF_T1	Summary Statistics (Absolute and Change from Baseline) : Body Weight		FA (SAC)
3.14.	ITT (Treated)	Non-Standard EFF_T2	Summary of Statistical Analysis (MMRM) Results of Change from Baseline: Body Weight	Include related estimated LSMeans and treatment differences.	FA (SAC)
Hypoglycemic & Hyperglycemic Events					
3.15.	ITT (Treated)	Non-Standard EFF_T3	Summary of Hypoglycaemic & Hyperglycaemic Events by Intensity, SAE Status, Relationship to Investigational Product and Withdrawal Status		FA (SAC)
Responder Status					
3.16.	ITT (Treated)	Non-Standard EFF_T4	Number and Percent of Subjects Meeting Definition of Glycemic Responder	Include Partial Remission Status and Hba1c responder status	FA (SAC)
3.17.	ITT (Treated)	Non-Standard EFF_T4	Number and Percent of Subjects Meeting Definition of C-Peptide Responder		FA (SAC)

11.10.8. Efficacy Figures

Efficacy Figures					
No.	Population	IDSL No. / E.G. Shell	Title	Programming Notes	Deliverable Priority
Mixed Meal Tolerance Test : Weighted Mean AUC(0-120 mins) C-Peptide & Glucose					
3.01	ITT (Treated)	Non- Standard EFF_F1	Model Adjusted Mean (+/- SE) Change from Baseline Plot : C-Peptide & Glucose Weighted Mean AUC(0-120 mins) from Mixed Meal Tolerance Test	By : Parameter X-Axis : Continuous scale for visit (months) Y-Axis : Mean (+/- SD) Chg from BL : Continuous scale for visit (months) Legend : Treatment	FA (SAC)
Clamp (Hyperglycaemic Phase) : Weighted Mean AUCs (60-140 & 0-140 mins) C-Peptide & Glucose					
3.02	ITT (Treated)	Non- Standard EFF_F1	Model Adjusted Mean (+/- SE) Change from Baseline Plot : C-Peptide Weighted Mean AUCs (60-140 mins) from Hyperglycaemic Clamp Test	As Figure 3.01, adapted accordingly to the data	FA (SAC)
Mean Daily Insulin Use					
3.03	ITT (Treated)	Non-Standard EFF_F1	Model Adjusted Mean (+/- SE) Change from Baseline Plot : Mean Daily Insulin Use	As Figure 3.01, adapted accordingly to the data	FA (SAC)
%HbA1c					
3.04	ITT (Treated)	Non- Standard EFF_F1	Model Adjusted Mean (+/- SE) Change from Baseline Plot : %HbA1c	As Figure 3.01, adapted accordingly to the data	FA (SAC)
Hyperglycemic and hypoglycemic events by month					

Efficacy Figures					
No.	Population	IDSL No. / E.G. Shell	Title	Programming Notes	Deliverable Priority
3.05	ITT (Treated)	EFF_F2	Mean (+/- SE) Number of hyperglycemic and hypoglycemic events by month		FA (SAC)

11.10.9. Pharmacodynamic Tables

Pharmacodynamic : Tables					
No.	Population	IDSL / TST ID / Example Shell	Title	Programming Notes	Deliverable [Priority]
Pharmacodynamic					
4.01.	Safety	Non- Standard PD_T1	Summary Statistics (Absolute and Change from Baseline): Target Engagement	For parameters with imputation please also include no. of subjects with LLQs & ULQ. Include the parameters to be summarized from 11.5.5 and also show the two derived % Target Engagement variables	FA (SAC)

11.10.10. Pharmacodynamic Figures

Pharmacodynamic : Figures					
No.	Population	IDSL / TST ID / Example Shell	Title	Programming Notes	Deliverable [Priority]
Pharmacodynamic					
4.01.	Fully Treated	Non- Standard EFF_F1	Mean (+/- SE) Change from Baseline in Target Engagement	Pages BY parameters, same as table. Lines by group. Please show same parameters as in Table 4.01.	FA (SAC)

11.10.11. Biomarker Tables

Biomarker : Tables					
No.	Population	IDSL / TST ID / Example Shell	Title	Programming Notes	Deliverable [Priority]
Biomarker					
5.01.	Fully Treated	Non- Standard EFF_T1	Summary Statistics (Absolute and Change from Baseline): Frequency and phenotype of lymphocyte subsets by flow cytometry		FA (SAC)
5.02.	Fully Treated	EFF_T5	Summary Statistics (Absolute and Change from Baseline): Frequency and phenotype of lymphocyte subsets by flow cytometry by C-Peptide Response		FA (SAC)
5.03.	Multimer Analyses	Non- Standard EFF_T1	Summary Statistics (Absolute and Change from Baseline): Frequency and phenotype of HLA-A2-restricted EBV-specific CD8+ T cells by multimer analysis		FA (SAC)
5.04.	Fully Treated	Non- Standard EFF_T1	Summary Statistics (Absolute and Change from Baseline): Quantification of serum cytokines and soluble cytokine receptors		FA (SAC)
5.05.	Fully Treated	Non- Standard EFF_T1	Summary Statistics (Absolute and Change from Baseline): TCR deep sequencing		FA (SAC)

11.10.12. Biomarker Figures

Biomarker : Figures					
No.	Population	IDSL / TST ID / Example Shell	Title	Programming Notes	Deliverable [Priority]
Biomarker					
5.01.	Fully Treated	EFF_F3	Mean (+/- SE) Change from Baseline in Frequency and phenotype of lymphocyte subsets by flow cytometry by C-Peptide Response		FA (SAC)

11.10.13. Pharmacokinetic Tables

Pharmacokinetic : Tables					
No.	Population	IDSL / TST ID / Example Shell	Title	Programming Notes	Deliverable [Priority]
PK Concentration					
6.01	Fully Treated	PK01	Summary of Free Serum Otelixizumab Concentration-Time Data by Treatment		FA (SAC)

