9.3.4. Pharmacokinetic Analyses

All free serum orelizumab concentration data will be graphically represented, descriptively summarised and listed appropriately.

Free serum orelizumab concentration time data will be analyzed by non-compartmental methods with WinNonlin Version 6.1 or higher. Calculations will be based on the nominal sampling times recorded during the study. From the serum concentration-time data, the following pharmacokinetic parameters may be determined, as data permit: maximum observed plasma concentration (C_{max}), time to C_{max} (t_{max}), area under the plasma concentration-time curve [$AUC(0-t)$ and $AUC(0-\tau)$], and apparent terminal phase half-life ($t_{1/2}$). Additional parameters may be included as required.

Pharmacokinetic data will be presented in graphical and/or tabular form and will be summarized descriptively. All pharmacokinetic data will be stored in the Archives, GlaxoSmithKline Pharmaceuticals, R&D.

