2.2. Study Objective(s) and Endpoint(s)

Primary	
Primary Objectives (Safety)	Primary Endpoints (Safety)

 To assess the effect of a single course of otelixizumab treatment on the acute and long term safety and tolerability of otelixizumab in NOT1DM patients. 	
 Incidence of adverse events (AEs) particularly those related to Cytokine release syndrome (CRS). Epstein-Barr virus (EBV) reactivation over Day 21 to Month 24. Changes in laboratory values, electrocardiograms (ECGs) and vital signs over Day 14 to Month 24.
Secondary	
Secondary Objectives (Pharmacokinetic)	Secondary Endpoints (Pharmacokinetic)

 To assess the pharmacokinetics of repeat dose administration of otelixizumab over 14 days in NOT1DM patients. 	
 Free serum otelixizumab concentrations over Days 1-14 and summary PK parameters.
Secondary Objectives (Efficacy)	Secondary Endpoints (Efficacy)

 To assess the effect of a single course of otelixizumab treatment on the rate of decline of pancreatic β-cell function over 24 months in NOT1DM patients. 	
 Change from baseline in C-peptide and glucose AUC (0-120) after a Mixed Meal Tolerance Test at Month 3, 6, 12, 18 and 24.

 To assess the effect of a single course of otelixizumab treatment on the rate of decline of C-peptide response and insulin sensitivity of β-cell function determined after a hyperglycemic clamp over 24 months in NOT1DM patients. 	
 Change from baseline in C-Peptide and glucose AUC hyperglycemic phase [H60 to H140 minutes] and insulin sensitivity (IS) index after a hyperglycemic clamp at Months 6 and 24.

 To assess the effect of a single course of otelixizumab treatment on exogenous insulin use for otelixizumab over 24 months in NOT1DM patients. 	
 Change from baseline in mean daily insulin use over 7 consecutive days during the week preceding all visits and phone calls.

 To assess the effect of a single course of otelixizumab treatment on glycaemic control over 24 months in NOT1DM patients. 	
 Change from baseline in HbA1c level. Body weight Day -1, Months 12-24. Hypoglycemic & hyperglycemic events over Months 1-24.

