4. ANALYSIS POPULATIONS

Population	Definition / Criteria	Endpoint(s) Evaluated
------------	-----------------------	-----------------------

Population	Definition / Criteria	Endpoint(s) Evaluated
Screened Population	
 All participants who were screened for eligibility 	
 Study Population Screening Failures
Randomized Population	
 All participants who were randomly assigned to a study treatment In summary tables, the treatment the subject was randomized to will be used 	
 Study Population
Enrolled Population	
 All participants who passed screening, signed informed consent and entered the study. This includes: 
 Run-in failures Randomised participants Screening failures are not included 	
 Assignment to Analysis Populations
Safety Population	
 Comprise of participants who receive at least one dose of study treatment. This population will be based on the treatment which the participant actually received. 	
 Study Population Safety Pharmacodynamic
Intent-To-Treat (Treated)	
 Comprise of all randomised participants who receive at least one dose of study treatment. This population will be based on the treatment to which the participant was randomised. 	
 Efficacy Biomarker
Per-Protocol Population (Treated)	
 Comprise of all randomized participants who receive at least one dose of study treatment and who comply with the protocol. Protocol deviations that would exclude participants from the PP population are defined in the Protocol Deviation Management Plan (PDMP) Version 2.5, dated 25-Jul-2018. If the PDMP is updated after signature of the SAP and before database lock, then the newest version will be used instead. 	
 As required based on data and exclusion of participants.
Fully treated	
 Comprise of all randomized participants who receive the full 6 days of treatment based on actual exposure data. 	
 Population may also be used for the key efficacy endpoints Population may be used for PK and biomarker analyses

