Multimer Analyses Population	
 Comprises of all Intent-to-treat (Treated) who have available multimer data 	
 Biomarker (Multimer Analysis)
NOTES :		

Population	Definition / Criteria	Endpoint(s) Evaluated

 • Please refer to Appendix 10: List of Data Displays, which details the population for each display generated. • As there are no planned pharmacokinetic analyses, this population will be defined for the next reporting effort. 		

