8.2. Derived Serum Pharmacokinetic Parameters

- Free serum orelizumab pharmacokinetic parameters will be calculated using SAS. Calculations will be based on the actual sampling times recorded during the study.
- From the serum concentration-time data, the pharmacokinetic parameters in [Table 2](#) will be determined for free serum orelizumab, as data permit, for each treatment and for each participant.
- Table 2 Derived Pharmacokinetic Parameters**

Parameter	Parameter Description
C _{max}	Maximum observed serum concentration
t _{max}	Time to C _{max}
AUC(0-τ)	Area under the serum concentration-time curve from time zero over the dose interval

NOTES: Additional parameters may be included as required.

AUC(0-τ) will be calculated using the trapezoidal rule (see section [11.5.4](#)) and will use all timepoints up to and including Day 6, 1 hour post dose.

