22.	Safety	AE8	Listing of All Adverse Events – Considered Potentially Associated with EBV Reactivation	
 See Section 11.5.3 for definition 	FA (SAC)
23.	Safety	OTHER_L12	Listing of Epstein-Barr Virus Serology: IgG & IgM and Viral Load: PCR	Please include the following: EBCIGGAS, EBVMSOS, EBCIGGAB, EBVMABZ, EBCIGMAB, EBVDNA	FA (SAC)
LABS					
24.	Safety	LB5	Listing of All Haematology Laboratory Data for Subjects with Abnormalities of Potential Clinical Importance		FA (SAC)
25.	Safety	LB14	Listing of Haematology Laboratory Data with Character Results		FA (SAC)
26.	Safety	LB5	Listing of All Clinical Chemistry Laboratory Data for Subjects with Abnormalities of Potential Clinical Importance		FA (SAC)
27.	Safety	LB14	Listing of Clinical Chemistry Laboratory Data with Character Results		FA (SAC)
28.	Safety	LB5	Listing of All Serology Data		FA (SAC)
29.	Safety	LB14	Listing of Serology Data with Character Results		FA (SAC)
ECG's					
30.	Safety	EG3	Listing of ECG Values of Potential Clinical Importance		FA (SAC)
31.	Safety	EG3	Listing of All ECG Values for Subjects with Any Value of Potential Clinical Importance	Including change from Baseline	FA (SAC)

ICH : Listings					
No.	Population	IDSL / TST ID / Example Shell	Title	Programming Notes	Deliverable [Priority]
32.	Safety	EG5	Listing of Abnormal ECG Findings		FA (SAC)
Vital Signs					
33.	Safety	VS4	Listing of Vital Signs of Potential Clinical Importance		FA (SAC)
34.	Safety	VS4	Listing of All Vital Signs for Subjects with Values of Potential Clinical Importance		FA (SAC)
Pharmacokinetics					
35.	Safety	PK07	Listing of free serum concentration-Time Data		FA (SAC)

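### The secondary pharmacokinetic endpoint is not fully delivered: no planned display shows Cmax, tmax or AUC, and every PK summary and plot leaves out patients stopped before Day 6.

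*SAP*

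**What the plan says.** SAP 2.2 gives the secondary PK endpoint as "Free serum otelixizumab concentrations over Days 1-14 and summary PK parameters". SAP 8.2 lists Cmax, tmax and AUC(0-tau) and says that they "will be determined for free serum orelizumab, as data permit, for each treatment and for each participant". Protocol 9.3.4 is softer on derivation ("the following pharmacokinetic parameters may be determined, as data permit") but has PK data presented and summarised descriptively.

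SAP Appendix 10 fixes what is produced and in which population. Its PK content is:

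- Table 6.01, "Summary of Free Serum Otelixizumab Concentration-Time Data by Treatment", in Fully Treated;
- Figures 6.01 to 6.03 (individual, mean and median concentration curves), in Fully Treated;
- Listing 35, "Listing of free serum concentration-Time Data", in Safety.

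SAP 4 defines Fully Treated as follows: "Comprise of all randomized participants who receive the full 6 days of treatment based on actual exposure data". It allows this population for PK and biomarker work. The notes to the same section add: "As there are no planned pharmacokinetic analyses, this population will be defined for the next reporting effort".

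**The concern.** There are two gaps. The first is that half of a secondary endpoint is defined and derived but has no output. A team that followed the display list exactly would finish the report with no exposure parameter by dose.

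The second is the population. A Day 1 concentration cannot depend on whether the patient later reaches Day 6. Requiring six days of treatment therefore selects Day 1 exposure on a later tolerability outcome. The trial looks for a tolerable dose, so exposure in patients who did not tolerate treatment is of direct interest. Those patients would appear in no PK summary or plot.

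The SAP 4 note suggests how this arose. It defers the PK population to a later report, yet this SAP covers the final analysis (SAP 3.2). No PK population is defined.

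**Working it through.** **Display count (SAP 11.10.13 to 11.10.16).**

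| Display | Population | Content | Cmax, tmax or AUC? |
|---|---|---|---|
| Table 6.01 | Fully Treated | concentrations | no |
| Figure 6.01 | Fully Treated | concentrations | no |
| Figure 6.02 | Fully Treated | concentrations | no |
| Figure 6.03 | Fully Treated | concentrations | no |
| Listing 35 | Safety | concentrations | no |

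Displays with a derived parameter: 0 of 5. Tables and figures on Fully Treated: 4 of 4. Displays that keep early stoppers: 1 of 5. SAP 9.3 puts PK/PD analysis outside the plan, so nothing there fills the gap.

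**What an early stopper contributes.** Under the Protocol 6.2.3 schedule, Day 1 is the only serially sampled day. Days 2-5 have a pre-dose sample only, Day 6 has pre-dose and 1 h, and Day 14 has one sample. Protocol 5.3.1 stops a patient who meets an individual CRS criterion immediately and permanently. Protocol 4.5 does not replace such patients and asks for PK sampling to continue where possible. So a patient stopped on Days 2-5 has the Day 1 profile but is not Fully Treated.

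**The parameters as defined.** Cmax and tmax carry no day. Samples around the end of an infusion exist on Day 1 (9 or 12 h infusion) and Day 6 (1 h infusion), so a course-wide Cmax could come from either of two very different infusions. AUC(0-tau) is defined in SAP 8.2 over the dose interval, but the note there integrates through Day 6 plus 1 h. The two are not the same quantity, and the second cannot be obtained for a patient not sampled to Day 6.

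**How many patients at 27 mg.** SAP 2.3 says that escalation stopping criteria were met in Cohort 3 but not which ones. Taking 8 active patients:

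- EBV rule (Protocol 5.3.2, assessed at about 6 weeks): possibly 0 stopped early.
- CRS Scenario IV (Protocol Table 6): at least 1 met an individual criterion, 1/8 = 12.5%.
- CRS Scenarios I-III: at least 3 met an individual criterion, 3/8 = 37.5%.

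These count patients who met a criterion. Fewer are lost from Fully Treated if a criterion was met only after the Day 6 infusion.

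**Possible bias in mean Day 1 concentration.** The documents give neither a between-patient CV nor an exposure-intolerance correlation, so both are assumed. For each cohort of 8, log-normal exposure is X = exp(sZ - s²/2) with s = √ln(1 + CV²), which is 0.294 at CV 30% and 0.472 at CV 50%. The intolerance score is S = rZ + √(1 - r²)E, where Z and E are independent standard normals. Remove the k patients with the highest S and divide the mean of the rest by the mean of all 8, by simulation:

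| CV | r | 1 of 8 removed | 3 of 8 removed |
|---|---|---|---|
| 30% or 50% | 0 | 1.000 | 1.000 |
| 30% | 0.3 | 0.981 | 0.951 |
| 30% | 0.5 | 0.968 | 0.918 |
| 50% | 0.3 | 0.969 | 0.921 |
| 50% | 0.5 | 0.946 | 0.867 |

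Subtracting 1 gives 0% at zero correlation, about -2% to -5% with one patient removed, and about -5% to -13% with three removed.

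**The case against.** The best defence is that PK here is secondary and descriptive, with no hypothesis to protect. SAP 4 openly allows Fully Treated for PK, and one fixed set of patients keeps mean curves from changing composition over the days. The concentration half of the endpoint does have a table, three figures and a listing. Listing 35 uses Safety, so early stoppers' raw values are reported. The SAP 4 note reads like text left over from an interim plan.

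Much of this stands. It limits the point to an endpoint not fully delivered, and it supports keeping Fully Treated as a supportive view. It does not supply a display for the parameters, and it gives no reason to condition Day 1 data on Day 6. Table 4.01 summarises target engagement, sampled at the same times, in Safety, so a broader population is workable.

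A reader might also infer that at least three of eight patients at 27 mg are dropped. The documents do not support that: one Scenario IV patient is enough for the CRS rule, the EBV rule may remove nobody, and the rule that was met is not stated. Nor do they show that exposure at the top dose will look flattened. They link CRS to dose and infusion speed, not to differences in exposure between patients on the same dose.

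**Conclusion.** The point holds as a gap in delivery and a poor choice of population. What rests on the documents alone is this: 0 of 5 PK displays show a parameter, 4 of 4 tables and figures require six days of treatment, and SAP 4 contradicts SAP 8 on whether PK is analysed. The missing parameters and the contradiction stand even if nobody stopped early.

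The size of the population effect is not known. The number of early stoppers at 27 mg is not given, and the bias figures illustrate assumed values of CV and correlation; they are not estimates for this trial.

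Two stronger readings should be avoided. The endpoint is not wholly undelivered, since concentrations are displayed. And the loss of a full Day 1 profile applies only to patients stopped after Day 1 sampling, not to anyone stopped during the Day 1 infusion. The change should be made, but the primary safety analysis does not depend on it.

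**What to change.** 1. Add a PK-parameter table and a matching listing by dose, in all otelixizumab-treated Safety participants with at least one post-dose concentration. State the day for each entry: Day 1 Cmax and tmax, pre-dose concentrations on Days 2-6, and the Day 6 1 h concentration. Report AUC only once SAP 8.2 says which interval it means, and show the course-long version only for patients sampled through Day 6 plus 1 h.
2. Base Table 6.01 and Figures 6.01-6.03 on the same population or, at the least, add a Day 1 summary and plot in it. Keep all samples, including Day 14, and flag those taken after permanent discontinuation. Show n at each time point. Keep Fully Treated as the supportive version.
3. Delete the SAP 4 note and define the PK population there.

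The cost is SAP wording plus one table and one listing from data already collected. The downside is that n and the mix of patients vary across time points, which is why n must be shown and the Fully Treated version kept.
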